### Statistical analysis plan

For the profiling of patients, quantitative variables (e.g. age, inflammatory scores, and GAGS scores) will be summarized using the mean and standard deviation or median and range (Min-max) if the data appears scattered. Meanwhile, qualitative variables (e.g. sex, examiner's assessment, patient's self-assessment) will be described as frequencies and percentages. The point and 95% confidence interval estimate of the mean inflammatory scores and GAGS scores

of the two treatment groups will be measured at baseline, at one month, and at the end of the trial. Lastly, independent two-sample t-test will be used to compare the two treatment groups in terms of: 1) the mean change in the inflammatory scores from baseline to end of the trial; 2) the mean change in the GAGS scores from baseline to end of the trial. Alternatively, Mann-Whitney U-Test will be used as an alternative if the data will be dispersed. Repeated measures ANOVA will be used to compare the inflammatory score and GAGS score of acne vulgaris patients on initial consult, at 4 weeks, and at 8 weeks. Friedman test will be used as a non-parametric alternative.

A 5% level of significance will be used in this hypothesis testing. SPSS version 25.0 will be used for all output and the necessary descriptive and inferential statistics in this study.

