#### **Inclusion Criteria**

- Filipino patients, aged 18-27 years old
- New patients diagnosed with Acne Vulgaris and a Global Acne Grading System score of at least 19
- Able to read and write in English or Tagalog
- Seen at the Out-Patient Department of East Avenue Medical Center Department of Dermatology

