### **Study Procedure**

1. In the Dermatology Out-Patient Department of East Avenue Medical Center, new patients who were diagnosed to have Acne Vulgaris, will be screened if they meet the inclusion/exclusion criteria.
2. Informed consent will be obtained for those who are qualified.
3. Patients will be given proper treatment whether they agree to participate or not. Patients who agree to participate will fill out an information sheet and three resident physicians will assess the patient's Global Acne Grading System (GAGS) and acne inflammatory score on initial visit, after 1 month, and after 2 months.
4. Patients will be given the bottle of zinc gluconate or placebo to be taken for 2 months, with patient education and a daily monitoring sheet. Details of blinding and randomization detailed below. Patients will be asked to follow up every 2 weeks where assessment and pill count will be done. Participants will be advised to continue intake if there are any unconsumed capsules within the 60-day period.
5. Data collected will be tabulated by the investigators and data analysis will be done.

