### **Treatment allocation and blinding**

The Solgar Zinc Gluconate 50mg will be repackaged by the TARC Pharmacy Laboratory of the University of Santo Tomas into the clear size 0 capsules. The same laboratory will prepare the placebo capsules and package the cornstarch placebo into the same clear size 0 capsules. This repackaging is necessary to ensure that the physicians and the participants will be blinded during the study. The capsules will be packaged in uniform airtight containers with 60 capsules per container. A third person not directly involved in care and assessment of the subjects, who also did the randomization, will be tasked to encode the capsules into groups A and B. Bottles will be labelled with the corresponding patient number only. Both the physician in charge and the patients will be unaware of which capsules contain Zinc Gluconate or placebo. During the study, patients will be asked to draw a number from 1 to 32, and he/she will get the corresponding bottle. The code will then be revealed during the data analysis portion to allow the statistician to segregate the results into the proper groups.

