### Sample Size Computation

The sample size is computed using G\*Power software. The effect size used was based on “Low Doses of Zinc Gluconate for Inflammatory Acne” by Dreno, P et al. (1989). According to this, the inflammatory score was statistically lower in the Zinc group than in the Placebo group at 2nd month of observation with p-value less than 0.02. The computed effect size was 0.6708327, this was used given that there was no effect size convention available in G\*Power for repeated measures between factors (ANOVA, F-test). The computed sample size of 12 (6 per group) was estimated using 0.05  $\alpha$ -level of significance at 80% actual power of analysis. Twenty percent of the computed sample size was added to adjust for the dropout rate. Thus, the minimum required sample size is 15. The sample sizes for power of analysis are shown in Table I.

Power of Analysis	Sample Size	Group 1	Group 2
99%	24	12	12
95%	18	9	9
90%	16	8	8
80%	12	6	6

Table I. Sample sizes for power of analysis

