## DUMMY TABLES

*Table 2. Demographic profile of patients*

	Zinc Gluconate (n= )		Placebo (n= )	
	Mean	SD	Mean	SD
Age in years				
	Frequency	Percentage	Frequency	Percentage
Sex				
Male				
Female				

*Table 3. Mean Inflammatory Scores*

Period	Mean Inflammatory Scores			
	Zinc Gluconate (n= )		Placebo (n= )	
	Mean	SD	Mean	SD
Initial				
Month 1				
Month 2				

*Table 4. Mean GAGS Scores*

Period	Mean GAGS Scores			
	Zinc Gluconate (n= )		Placebo (n= )	
	Mean	SD	Mean	SD
Initial				
Month 1				
Month 2				

*Table 5. Comparison of two treatment groups in terms of mean change in the inflammatory scores and GAGS scores from baseline to end of the trial*

Mean change of outcomes from baseline to end of the trial					
Outcomes	Zinc Gluconate (n= )		Placebo (n= )		p value
	Mean	SD	Mean	SD	

Inflammatory Score			
GAGS score			

Table 6. Frequency of each category for examiner's assessment

Examiner's Assessment of Improvement of Acne				
Assessment	Zinc Gluconate (n= )		Placebo (n= )	
	Frequency	Percentage	Frequency	Percentage
No Improvement				
Slight Improvement (<50%)				
Marked Improvement (≥50%)				

Table 7. Frequency of each category for patient's self-assessment

Patient's Self-Assessment of Improvement of Acne				
Assessment	Zinc Gluconate (n= )		Placebo (n= )	
	Frequency	Percentage	Frequency	Percentage
No Improvement				
Slight Improvement (<50%)				
Marked Improvement (≥50%)				

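### The arms are compared by a t-test on change with no baseline adjustment; ANCOVA on the baseline score already collected would usually be more precise at almost no cost

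*Combined protocol and SAP*

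**What the plan says.** The Outcome measures section makes the change in the inflammatory and GAGS scores, from first consult to end of trial, the primary outcome. The Statistical analysis plan never labels a test as primary, but its only stated comparison of the arms on that outcome is that an "independent two-sample t-test will be used to compare the two treatment groups in terms of: 1) the mean change in the inflammatory scores", with the same test for GAGS. The fallback is that "Mann-Whitney U-Test will be used as an alternative if the data will be dispersed".

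The same section adds that "Repeated measures ANOVA will be used to compare the inflammatory score and GAGS score of acne vulgaris patients on initial consult" and at two later visits. It names neither treatment arm nor a baseline covariate for that model, and does not say how the model ranks beside the t-test.

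The baseline values exist: the Study Procedure has three physicians record GAGS and the "acne inflammatory score on initial visit, after 1 month, and after 2 months". Table 5 of the Dummy Tables, titled "Comparison of two treatment groups in terms of mean change in the inflammatory scores and GAGS scores from baseline to end of the trial", has a mean and SD of change per arm and a p value. It has no column for the difference between arms or its confidence interval.

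**The concern.** The trial is small. The Sample Size Computation sets a minimum of 15 patients, and under Treatment allocation and blinding "patients will be asked to draw a number from 1 to 32", so the planned size lies between 15 and 32. At that size, precision per patient counts.

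A change score uses baseline only by subtraction, which sets the coefficient of baseline to 1. That is optimal only if the true regression slope of the month-2 score on baseline is 1. Otherwise the comparison carries avoidable noise. The repeated measures ANOVA does not remove it, because it treats the first visit as one of the outcomes.

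Timing matters too. The code is broken at the analysis stage, and a covariate added after that would be a data-driven choice. The plan already leaves one such choice open, because the switch to Mann-Whitney has no criterion and the final test can be picked after seeing the data.

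**Working it through.** **The plan's own figure.** The Sample Size Computation states that "The computed effect size was 0.6708327", entered in a repeated measures between-factors F-test. Reading it as Cohen's f, the noncentrality is f² × N × m / (1 + (m − 1) × r), with 1 and N − 2 degrees of freedom. With m = 3 visits and an assumed r = 0.3, N = 12 gives 0.6708327² × 12 × 3 / 1.6 = 10.1 and power 0.818. Power at N = 16, 18 and 24 is 0.927, 0.955 and 0.990, so every row of Table I is reproduced. The plan does not state r; 0.3 is inferred. Read instead as d (f = 0.335), power at N = 12 is at most 0.44 for any non-negative r, so f is the more likely reading. For two equal groups, d = 2f = 1.34.

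**Variance formulas.** Set the baseline SD to 1, the month-2 SD to k, and their correlation to ρ.
- Change: 1 + k² − 2ρk.
- ANCOVA: k²(1 − ρ²) × (1 + 1/(N − 4)). The last factor is the price of estimating the slope: 1.036 at N = 32 and 1.125 at N = 12.
- The best slope is ρk, so change is optimal only when ρk = 1.

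Example with k = 1, ρ = 0.5: change has variance 1.00. ANCOVA has 0.75 × 1.036 = 0.777 at N = 32 (22% lower) and 0.75 × 1.125 = 0.844 at N = 12 (16% lower).

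**Variance reduction in %, ANCOVA against change** (negative = loss; ρ and k are assumptions):

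| k | N | ρ 0.3 | 0.5 | 0.7 | 0.8 | 0.9 |
|---|---|---|---|---|---|---|
| 0.75 | 32 | 52 | 46 | 42 | 42 | 48 |
| 0.75 | 12 | 48 | 42 | 37 | 37 | 43 |
| 1 | large | 35 | 25 | 15 | 10 | 5 |
| 1 | 32 | 33 | 22 | 12 | 7 | 2 |
| 1 | 15 | 29 | 18 | 7 | 2 | −4 |
| 1 | 12 | 27 | 16 | 4 | −1 | −7 |
| 1.25 | 32 | 19 | 8 | −2 | −4 | 2 |
| 1.25 | 12 | 12 | 0 | −10 | −12.5 | −7 |

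At k = 1 the break-even correlation is 0.78 for N = 12, 0.83 for N = 15 and 0.93 for N = 32. At k = 1 and ρ = 0.3, 0.5 and 0.7, the mean 95% CI is 18, 12 and 6% narrower at N = 32, and 14, 7 and 1% narrower at N = 12.

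**Power in %, t-test on change → ANCOVA** (k = 1, d in month-2 SDs, two-sided 5%, 40,000 simulated bivariate normal trials per cell; type I error close to 5% for both tests):

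| Per arm | d | ρ 0.3 | 0.5 | 0.7 | 0.8 |
|---|---|---|---|---|---|
| 6 | 1.34 | 42 → 54 | 56 → 62 | 77 → 78 | 91 → 90 |
| 16 | 1.34 | 87 → 96 | 96 → 99 | >99 both | >99 both |
| 6 | 0.67 | 14 → 18 | 18 → 21 | 27 → 28 | 38 → 38 |
| 16 | 0.67 | 34 → 47 | 45 → 55 | 66 → 71 | 83 → 85 |

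Sixteen per arm assumes that the 32 bottles are split equally. In an unfavourable case (k = 1.25, ρ = 0.7), power goes from about 82 to 78% (6 per arm, d = 1.34) and from 72 to 71% (16 per arm, d = 0.67).

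**Entry threshold on GAGS.** The Inclusion Criteria require "New patients diagnosed with Acne Vulgaris and a Global Acne Grading System score of at least 19", which narrows the baseline GAGS spread. Hold the slope at 0.5 and the residual variance at 0.75, and let V be the baseline variance. The large-sample reduction is 0.25V / (0.75 + 0.25V). For V = 1 it is 0.25/1.00 = 25%; for V = 0.75, 0.1875/0.9375 = 20%; for V = 0.5, 0.125/0.875 = 14%. With the slope penalty, the V = 0.5 case gives 11% at N = 32 and 4% at N = 12. How far the threshold cuts the variance is unknown.

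**The case against.** The t-test on change is a legitimate analysis. It matches the outcome as defined, it is unbiased under randomisation, and it already uses baseline by subtraction. All of that stands, and it is why this is advice on efficiency and not a correction.

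ANCOVA can also lose. At N = 12 with equal SDs it is less precise once the correlation passes 0.78, and with k = 1.25 and a correlation of 0.8 the loss is 12.5%. This stands too. However, 12.5% is the whole slope penalty at N = 12 and so the ceiling on the loss; at N = 32 the ceiling is 3.6%.

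The effect size is best read as d = 1.34. With 16 per arm the planned test then already has 87% power or more at correlations of 0.3 and above with equal SDs. The larger power gains at that size belong to the d = 0.67 reading and show what happens if the true effect is smaller than planned. Even so, at d = 1.34 ANCOVA raises power from 87 to 96% at a correlation of 0.3, and the narrower interval does not depend on the effect size.

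Lastly, a month-2 score as the dependent variable departs from the plan's wording about change. This is easily met: ANCOVA of change on arm and baseline gives the identical treatment estimate.

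**Conclusion.** The point holds as a worthwhile improvement, not an error. No baseline-adjusted comparison is planned, although the scores are collected. With equal SDs and correlations of 0.3 to 0.7, ANCOVA lowers the variance of the zinc minus placebo difference by 12 to 33% at N = 32 and by 4 to 27% at N = 12. If the SD falls to 0.75 of baseline, the reduction is 37 to 52% over the same correlations and sizes. Losses arise only when ρk is near 1, and they matter mainly at the smallest sizes.

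These figures rest on assumed correlations and SD ratios and a normal model. The 0.3 that reproduces Table I would favour ANCOVA, but it is an inference. For GAGS the gain may be smaller because of the entry threshold.

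**What to change.** Before the code is broken, amend the Statistical analysis plan as follows.

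- Make the primary analysis an ANCOVA of the month-2 inflammatory score on treatment arm with the baseline inflammatory score as covariate. Use the same model for GAGS with its own baseline. To keep the wording about change, use change as the dependent variable with the same terms; the treatment estimate is the same.
- Add to Table 5 the adjusted zinc minus placebo difference with its 95% CI.
- Delete the data-dependent switch, and keep Mann-Whitney on the change as a sensitivity analysis only.
- State that the repeated measures ANOVA over the three visits is supportive.

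The cost is SAP wording and one table column, with no new data, visits or patients. Statistically it costs one residual degree of freedom (30 to 29 at N = 32, 10 to 9 at N = 12) and the slope penalty of 3.6% or 12.5% in variance, which is already included in the finite-sample figures above.

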### **Intervention**

Patients will be randomly assigned to 60 days of oral Zinc Gluconate capsules (one capsule of 200mg daily) versus the placebo capsules. The participants will be given a container filled with 60 capsules. They will be instructed to take 1 capsule once a day 20 minutes before the morning meal in their residence. The starch placebos will be identical to zinc supplements in size, color, and shape hence both patients and investigators will be unable to tell whether participant will be on zinc supplementation or placebo.

All participants will receive the same adapalene 0.3% + benzoyl peroxide 2.5% preparation to be applied two times a day on affected areas. Patient education on Acne Vulgaris, Zinc sources, and basic skin care will be performed on all patients. Instructions will be given to avoid intake of other medication or supplementation during the 60-day trial.

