### **Outcome measures**

The primary outcome measure will be the change in inflammatory scores, GAGS scores of the zinc and placebo groups from initial consult to the end of the trial. The secondary outcome measures include the examiner's assessment score and the patient's self-assessment score.

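### The repeated-measures ANOVA is worded as a comparison of visits and its Friedman fallback cannot include arm, so neither adds to the planned change-score test of zinc against placebo, and neither matches the test used to size the trial

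*Combined protocol and SAP*

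**What the plan says.** Three places bear on this point.

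- **Between-arm test (Statistical analysis plan).** The "independent two-sample t-test will be used to compare the two treatment groups in terms of" change from baseline to end of trial in each of the two scores. The rank fallback is stated as "Mann-Whitney U-Test will be used as an alternative if the data will be dispersed". In Outcome measures, the endpoint that this serves is worded as "The primary outcome measure will be the change in inflammatory scores, GAGS scores of the zinc and placebo groups from initial consult"; the interval closes at the final visit.
- **Repeated-measures analysis (same section, next sentences).** The sentence reads "Repeated measures ANOVA will be used to compare the inflammatory score and GAGS score of acne vulgaris patients on initial consult, at 4 weeks"; week 8 is the third visit listed. No arm factor or arm-by-visit term is named. Then: "Friedman test will be used as a non-parametric alternative".
- **Sizing (Sample Size Computation).** The effect size of 0.6708327 is used for "repeated measures between factors (ANOVA, F-test", giving 12 patients for 80% power and 15 after the dropout allowance.

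Two design features matter as well. Under Intervention, "All participants will receive the same adapalene 0.3% + benzoyl peroxide 2.5% preparation". Under Inclusion Criteria, patients need a GAGS score of 19 or more.

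**The concern.** A repeated-measures ANOVA across visits, without arm, asks whether scores change over time. Friedman asks the same thing on ranks: it orders the visits within each patient and has no place for a between-patient factor. Pooled, it ignores arm. Run separately by arm, it gives two within-arm p-values and no comparison between them.

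Scores should fall over time in this trial for reasons unrelated to zinc. Both arms receive a topical combination that the protocol's own literature review describes as effective, and entry above a severity cut-off invites regression to the mean. A significant visit effect, or significance in the zinc arm alone, could therefore sit beside the real treatment comparison and be taken as support for zinc.

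There is also a mismatch. The trial was sized on a repeated-measures test of arm, but the only repeated-measures analysis in the SAP is worded as a test of time. As a result, the 4-week scores enter no formal treatment comparison.

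**Working it through.** **1. Which test does the sample size describe?** Inputs from Sample Size Computation: effect size f = 0.6708327 (read as Cohen's f; the type is not stated), α = 0.05, two groups. Assumed: m = 3 measurements and a common correlation ρ, neither of which is stated.

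Between-factors test: λ = f²·N·m / (1 + (m − 1)ρ), with 1 and N − 2 degrees of freedom. With f² = 0.4500 and ρ = 0.3, at N = 12, λ = 0.4500 × 12 × 3 / 1.6 = 10.125 and power is 0.818.

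| N | Power (between factors, m = 3, ρ = 0.3) | Table I target |
|---|---|---|
| 12 | 0.818 | 80% |
| 16 | 0.927 | 90% |
| 18 | 0.955 | 95% |
| 24 | 0.990 | 99% |

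These are the smallest even totals reaching each target, so Table I (12/16/18/24) is reproduced. The within-patient and interaction versions use λ = f²·N·m / (1 − ρ) with 2 and 2(N − 2) degrees of freedom. They give 6/8/8/10 at ρ = 0.5 and 8/10/10/14 at ρ = 0.3, and do not match. The values of m and ρ are inferred from the fit (m = 5 with ρ = 0.4 gives the same table), but the section itself names the between-factors test. The dropout step also reproduces: 12 / 0.8 = 15, and 12 × 1.2 = 14.4, rounded up to 15.

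**2. Which planned tests respond to arm?** Simulation, 16 per arm (an equal split of the 32 numbered bottles), ρ = 0.5, three visits, linear change, 4,000 runs. Entries are rejection rates at 5%.

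| Test | Both arms improve 1 SD, no zinc effect | Arm difference growing to 1 SD at week 8 |
|---|---|---|
| Visit-only ANOVA | 99.9% | about 100% |
| Friedman, pooled | 99.0% | about 100% |
| Arm main effect | 4.8% | 38% |
| Arm-by-visit | 5.2% | 69% |
| t-test on change | 5.4% | 78% |
| Mann-Whitney on change | 4.9% | 75% |

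The first two rows hardly move with the zinc effect. The arm main effect is weak because it averages in the baseline visit, where the arms do not differ.

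**3. How often would a zinc-only pattern arise by chance?** Assume no zinc effect, both arms improving by 0.5–1.5 SD, ρ = 0.3–0.5, and Friedman run by arm. The arms are independent, so P(zinc only) = p(1 − p), where p is the per-arm rejection rate. This cannot exceed 0.5 × 0.5 = 25%.

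- *8 per arm* (the minimum of 15, rounded up to equal arms): p runs from 0.12 to 0.82. The ends give 0.12 × 0.88 = 0.11 and 0.82 × 0.18 = 0.15, and the peak is near 0.25. The simulated range is about 10–25%. Pooled Friedman rejects in 23–99%.
- *16 per arm*: about 1–23% overall, falling to about 1–4% at 1.5 SD, where nearly every arm is significant. Pooled Friedman rejects in about 41–100%.

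In every setting the planned t-test on change rejected in about 5% of trials. A zinc-only pattern together with a significant t-test occurred in at most about 2%.

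**4. What would baseline adjustment gain?** With unit SD at each visit, the SD of a change score is √(2(1 − ρ)), while the residual SD after adjusting month 2 for baseline is √(1 − ρ²). At ρ = 0.5 these are 1.00 and 0.87; at ρ = 0.3, 1.18 and 0.95. For a 1 SD effect, simulated power was:

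| Per arm | t-test on change | Baseline-adjusted month 2 |
|---|---|---|
| 8 | 35–45% | 47–54% |
| 16 | 64–78% | 80–87% |

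Null rejection stayed near 5% for both.

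**The case against.** The strongest reply is that the visit comparison was never meant to test zinc. The specific objectives list the time course at initial consult, 4 and 8 weeks separately from the between-arm question, and the repeated-measures sentence echoes the former. For a time course, Friedman is the usual rank counterpart of one-way repeated-measures ANOVA. Among the dummy tables, only Table 5, the between-arm change comparison, has a p-value column. Nothing says that tests will be run by arm or that a visit effect will count for zinc. Month 1 is not ignored either, since estimates with 95% confidence intervals are planned for each arm.

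Much of this stands, and it rules out three stronger readings:

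- *That the SAP has no between-arm test.* It has one, it fits the primary outcome, and it holds its 5% level.
- *That the pooled rejection rates are false-positive rates for zinc.* They are power to detect a real improvement over time.
- *That a zinc-only pattern is a 10–25% risk whatever the enrolment.* That range holds at 8 per arm; at 16 it can be near 1%.

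The reply does not remove the mismatch with the sizing model. If arm was meant to be in the ANOVA, the sentence omits it and Friedman is the wrong fallback. If it was not, the trial was sized on a test the SAP does not run, and nothing labels the visit comparison as descriptive.

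**Conclusion.** The point holds in a limited form. The treatment question is covered by the t-test or Mann-Whitney on change. The repeated-measures ANOVA as worded, and Friedman by its nature, do not test zinc against placebo, and neither corresponds to the between-factors test behind the 12 patients.

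The consequence is a risk of misreading and some lost efficiency, not an invalid primary test. The zinc-only figures require that the test be run by arm, which the SAP does not say. All the simulated figures rest on assumed improvements, correlations, equal arms and a common correlation between visits. The conclusions about what ANOVA without arm, and Friedman, can test do not depend on those assumptions.

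**What to change.** In the Statistical analysis plan, replace the repeated-measures sentence and its fallback with the following:

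- For each score, a between-arm model of the month-1 and month-2 values with arm, visit, arm-by-visit and baseline score, reporting the month-2 arm difference with its 95% confidence interval. With two post-baseline visits an unstructured covariance has only three parameters. If that is thought fragile at about 8 per arm, use ANCOVA of the month-2 score on arm and baseline.
- A statement that this month-2 contrast is the primary treatment test, with the t-test on change as supportive.
- Mann-Whitney on change as the rank alternative.
- Friedman dropped, or it and any other visit comparison labelled within-patient and descriptive.

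Merely adding arm to the three-visit ANOVA and reading its main effect is not enough, for the power reason shown in step 2. Sample Size Computation should then name the same contrast as the SAP.

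The cost is a small rewording and slightly more analysis work in the SPSS version already specified. No new data, visits or patients are needed.
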